7.0 TRIAL PROCEDURES

7.1 Trial Procedures

The Trial Flow Chart - Section 6.0 summarizes the trial procedures to be performed at each visit. Individual trial procedures are described in detail below. It may be necessary to perform these procedures at unscheduled time points if deemed clinically necessary by the investigator.

Furthermore, additional evaluations/testing may be deemed necessary by the Sponsor and/or Merck for reasons related to subject safety. In some cases, such evaluation/testing may be potentially sensitive in nature (e.g., HIV, Hepatitis C, etc.), and thus local regulations may require that additional informed consent be obtained from the subject. In these cases, such evaluations/testing will be performed in accordance with those regulations.

7.1.1 Administrative Procedures

7.1.1.1 Informed Consent

The Investigator or delegate must obtain documented consent from each potential subject prior to participating in a clinical trial.

7.1.1.1.1 General Informed Consent

Consent must be documented by the subject's dated signature or by the subject's legally acceptable representative's dated signature on a consent form along with the dated signature of the person conducting the consent discussion.

A copy of the signed and dated consent form should be given to the subject before participation in the trial.

The initial informed consent form, any subsequent revised written informed consent form and any written information provided to the subject must receive the IRB/ERC's approval/favorable opinion in advance of use. The subject or his/her legally acceptable representative should be informed in a timely manner if new information becomes available that may be relevant to the subject's willingness to continue participation in the trial. The communication of this information will be provided and documented via a revised consent form or addendum to the original consent form that captures the subject's dated signature or by the subject's legally acceptable representative's dated signature.

Specifics about a trial and the trial population will be added to the consent form template at the protocol level.

The informed consent will adhere to IRB/ERC requirements, applicable laws and regulations and Sponsor requirements.

7.1.1.2 Inclusion/Exclusion Criteria

All inclusion and exclusion criteria will be reviewed by the investigator or qualified designee to ensure that the subject qualifies for the trial.

7.1.1.3 Medical History

A baseline medical history and physical exam will be collected from the medical record from standard clinical visits with the treating medical oncologist.

7.1.2 Clinical Procedures/Assessments

7.1.2.1 Adverse Event (AE) Monitoring

The investigator or qualified designee will assess each subject to evaluate for potential new or worsening AEs as specified in the Trial Flow Chart. Adverse events that are grade 3 or higher will be recorded. Adverse events related to the research PET/CT will only be assessed for the period of time from the injection of FDG to the completion of the imaging exam. AEs related to the clinical treatment will not be collected or reported as part of this study.

Please refer to section 7.2 for detailed information regarding the assessment and recording of AEs.

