2.0 TRIAL DESIGN

2.1 Trial Design

This is a single institution, prospective, observational cohort study of FDG PET/CT as an early measure of response in patients with advanced metastatic melanoma scheduled to start pembrolizumab. Patients may participate in this study if they are greater than 18 years of age; most participants will be receiving care at the clinical practices of the University of Pennsylvania. Patients that may meet eligibility criteria will be approached about study participation regardless of race or ethnic background.

We anticipate enrolling up to 35 participants with metastatic melanoma who meet eligibility requirements for this study. The target accrual goal is to reach 30 evaluable patients, defined as those who complete two (Baseline and 1st Post-therapy) of the three planned FDG PET/CT scans. Thus, accrual is estimated to occur over approximately 1 year.

FDG PET/CT imaging will be used to evaluate glycolytic activity at sites of metastatic disease using the FDA approved clinical Positron Emission Tomography (PET) radiotracer, [¹⁸F]Fluorodeoxyglucose (FDG). Study imaging will be performed in a manner identical to standard clinical FDG PET/CT imaging procedures used at the Hospital of the University of Pennsylvania using a dedicated whole-body PET/CT scanner. For each PET scan static images from the vertex of the skull to toes will be acquired approximately 60 minutes after injection of FDG. Imaging data will be processed as per standard protocol. The study will be performed under the regulatory approval of the Penn Institutional Review Board (IRB).

A total of three FDG PET/CT exams will be performed as follows:

- **Baseline:** A restaging FDG PET/CT will be obtained no more than 4 weeks prior to initiation of pembrolizumab to assess baseline, pre-therapy tumor glycolytic activity. This exam will be obtained for study purposes, although in some cases it may be obtained as clinical standard of care for restaging of disease prior to initiation of a new line of therapy. If this exam is obtained as clinical standard of care, it may occur prior to consent and enrollment in this study.
- **1st Post-therapy:** at approximately 3 weeks (\pm 3 weeks) following the start of pembrolizumab, a post-therapy FDG PET/CT will be obtained. This exam will be obtained for study purposes, to assess glycolytic activity at sites of metastatic disease at an early time-point.

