4.1.1 Dose Rationale and Risk/Benefits Assessment

2-Deoxy-2-[¹⁸F]fluoro-D-glucose (FDG) is FDA approved for imaging in clinical oncology, and has been extensively used in oncologic PET imaging with no evidence of pharmacological effect. No adverse events (AEs) have been reported in the large number of published studies of human experience for FDG at the dose to be used in this study. In this study we will administer approximately 15 mCi of FDG according to the standard procedures used for clinical FDG PET/CT at the Hospital of the University of Pennsylvania.

Risk/Benefit

Participants will undergo up to two additional FDG PET/CT examinations for the purposes of this study. This will be in addition to other clinically indicated CT and/or PET/CT examinations. FDG is a positron emitting radiopharmaceutical. As such, it poses an intrinsic radiation exposure risk. However, when administered in low tracer doses as a PET imaging agent, as described in this protocol, this risk is felt to be extremely small. In addition to the radioactive FDG tracer, a low-dose CT of the chest, abdomen and pelvis is typically performed with the FDG PET/CT for the purpose of anatomical registration and attenuation correction of PET images. There are no separate diagnostic CT scans performed as part of this scan. FDG PET/CT scans are a standard clinical procedure for patients with metastatic melanoma. This research involves exposure to radiation that could affect a fetus or pregnant woman, due to this risk a urine pregnancy test will be performed for women of childbearing potential at the time of screening. Women who are pregnant at the time of screening will not be included in this study.

The dose will be delivered intravenously by skilled clinical professionals who typically administer FDG for clinical purposes; venous cannulation is a routine clinical procedure that carries minimal risks when performed by trained personnel. It is possible that bruising, dizziness or fainting could occur in some subjects. There is a risk of phlebitis or infection, which is very remote. Also, the PET/CT scan takes place in a small, enclosed space and therefore can be uncomfortable for some people with claustrophobia or musculoskeletal disorders (such as arthritis). Subjects will be made as comfortable as possible and staff will be available throughout the imaging to address any discomfort.

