No psychological, social or legal risk is expected. While loss of confidentiality is possible, it is felt to be very unlikely due to the small number of professionals involved in the study with

knowledge of this information. All clinicians and research staff involved are well trained in HIPAA practices. There is no anticipated additional financial risk to the patient due to participation in this study since the two additional study FDG PET/CT's, 1 week blood draw (if performed), and post-therapy tumor biopsy (if performed) will be paid for through study funds. The clinical restaging FDG PET/CT examinations and pre-therapy tumor biopsy (if performed) will be paid for through the patient's insurance as per routine clinical care for their cancer. Additional blood draws described in this protocol outside of the 1 week sample will be paid for by the Penn Melanoma Tissue Collection Program.

The risk to the patient is felt to be minimal with only the added radiation considered the likely risk posed to the patient. It is not unusual for oncologic patients to receive multiple radiological tests, including multiple PET/CT scans, in the course of clinical management and the addition of two FDG PET/CT scans is not considered to add a large risk to the subject. This study proposes the addition of two PET/CT scans to the patient's care. This study also proposes the addition of one tumor biopsy to the patient's care; this procedure carries a low risk of bleeding or infection at the biopsy site, thus the additional risk to the patient from this procedure is felt to be minimal.

There is no anticipated benefit to study subjects as a result of their participation in this study. There is potential benefit to general society if FDG PET/CT proves to be a useful imaging agent for detecting an early response to immunotherapy for cancer, or helps in the understanding of pembrolizumab's mechanism of action.

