6.0 TRIAL FLOW CHART

6.1 Study Flow Chart

	Screening Phase	Baseline FDG PET/CT ⁴	1 st Post-therapy FDG PET/CT	Tumor Tissue Collection ⁵	2 nd Post-therapy FDG PET/CT ⁶
Scheduling window relative to pembrolizumab initiation:		< 4 weeks prior	3 weeks after (\pm 3 weeks)		> 10 weeks after
Administrative Procedures					
Informed Consent	X				
Inclusion/Exclusion Criteria	X				
Demographics and Medical History	X				
Clinical Procedures/Assessments					
Review Adverse Events ¹			X	X	
Laboratory Procedures/Assessments: analysis performed on site					
Pregnancy Test – Urine or Serum β -HCG	X				
Tumor Imaging and Assessment of Disease					
FDG PET/CT ²		X	X		X
Tumor Biopsies/Archival Tissue Collection/Correlative Studies Blood					
Archival or Newly Obtained Tissue Collection	X			X	
Correlative Studies Blood Collection ³					

¹Adverse events related to the research PET/CT will only be assessed for the period of time from the injection of FDG to the completion of the imaging exam. AEs related to the clinical treatment will not be collected or reported as part of this study.

²All FDG PET/CT scans will be performed as per routine clinical procedure.

³Less than 65 mL of blood will be collected after initiation of pembrolizumab according to the following schedule: weeks 0, 1, 3, 6, 9, 12, 15, and at 1 year; specimens will be processed and stored according to the Penn Melanoma Program tissue collection Standard Operating Procedure. The week 1 blood sample will be collected only for the purposes of this study. If blood samples cannot be collected they will be omitted and not considered a protocol deviation.

⁴This scan will usually be performed as a research exam. Occasionally, it may be performed as a clinically indicated restaging exam, which may occur prior to consent and enrollment in this study.

⁵Tumor tissue is to be collected within 7 days after the 1st Post-therapy FDG PET/CT. The biopsy techniques preferred for this study include core biopsies or surgical biopsies. The same biopsy techniques should be used as routinely used for a given tumor lesion/location and specimens will be processed and stored according to the Penn Melanoma Program

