7.2.1 Immediate Reporting of Adverse Events to the Sponsor and to Merck

7.2.1.1 Serious Adverse Events

A serious adverse event is any adverse event occurring during participation in this study that:

- Results in death;
- Is life threatening;
- Results in persistent or significant disability/incapacity;
- Results in or prolongs an existing inpatient hospitalization;
- Is a congenital anomaly/birth defect;
- Is an other important medical event

Refer to Table 6 for additional details regarding each of the above criteria.

For the time period beginning when the consent form is signed until the completion of the post-therapy tumor tissue biopsy any serious adverse event, or follow up to a serious adverse event, including death due to any cause other than progression of the cancer under study that occurs to any subject must be reported within 24 hours to the Sponsor and within 2 working days to Merck Global Safety if it causes the subject to be excluded from the trial.

Additionally, any serious adverse event, considered by an investigator who is a qualified physician to be related to the research FDG PET/CT scan procedure or post-therapy tumor tissue biopsy that is brought to the attention of the investigator at any time following consent through the end of the specified safety follow-up period specified in the paragraph above, or at any time outside of the time period specified in the previous paragraph also must be reported immediately to the Sponsor and to Merck Global Safety.

All subjects with serious adverse events must be followed up for outcome.

SAE reports and any other relevant safety information are to be forwarded to the Merck Global Safety [contact]

A copy of all 15 Day Reports and Annual Progress Reports is submitted as required by FDA, European Union (EU), Pharmaceutical and Medical Devices agency (PMDA) or other local regulators. Investigators will cross reference this submission according to local regulations to the Merck Investigational Compound Number (IND, CSA, etc.) at the time of submission. Additionally investigators will submit a copy of these reports to Merck & Co., Inc. (Attn: Worldwide Product Safety; [contact]) at the time of submission to FDA.

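### Adverse event review is not scheduled at the baseline research scan, and the scan window leaves out delayed non-serious events

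*Combined protocol and SAP*

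**What the plan says.** Section 7.1.2.1 has the investigator or a designee do the AE assessment by reference to the chart: the assessor "will assess each subject to evaluate for potential new or worsening AEs as specified in the Trial Flow Chart". It records events of grade 3 or higher only. It then limits scan-related events to the imaging session itself: "Adverse events related to the research PET/CT will only be assessed for the period of time from the injection of FDG to the completion". Footnote 1 to the chart in 6.1 repeats this limit.

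In 6.1, the row "Review Adverse Events" is marked under the 1st post-therapy PET/CT and under tumor tissue collection. The screening, baseline and 2nd post-therapy columns are blank. Footnote 4 says the baseline scan is normally done for research and only occasionally as clinical restaging. Section 4.1.1 counts the exposures in the same way: "Participants will undergo up to two additional FDG PET/CT examinations for the purposes of this study".

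On risks of the scan, 4.1.1 mentions bruising, dizziness and fainting, and adds: "There is a risk of phlebitis or infection, which is very remote". On the biopsy it says "this procedure carries a low risk of bleeding or infection at the biopsy site".

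Section 7.2 defines an AE broadly, as an event associated in time with a protocol procedure whether or not it is related. It also applies standard AE reporting once a consented subject needs a blood draw or fresh biopsy. Section 7.2.1.1 makes any serious event reportable from consent "until the completion of the post-therapy tumor tissue biopsy". A serious event judged related to the research scan or the biopsy is reportable whenever it reaches the investigator, including after that period.

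**The concern.** The study adds up to two research FDG injections per participant, and the schedule asks about AEs at only one of them. Because 7.1.2.1 defers to the chart, a blank cell is an instruction not to schedule a review there.

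The time limit raises a second question. A window that ends with the imaging session cannot include an event that develops afterwards, and two of the scan risks that the protocol names would mostly do so. The protocol evidently means to record non-serious events of grade 3 or higher, since it sets that threshold. For delayed events of this kind, footnote 1 and 7.1.2.1 give no time at which they would be recorded. Treatment-related AEs are excluded from collection, so procedure-related events are the main safety information that this study will hold.

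**Working it through.** The protocol states no figure on this point, so the check is a comparison of passages, with a simple count for scale.

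**1. Are the chart marks in the right columns?** The FDG PET/CT row has marks under baseline, 1st post-therapy and 2nd post-therapy, which matches the three scans in 2.1. The tissue row has marks under screening and tissue collection, which matches the archival and post-therapy samples. Read in the same way, the AE row has marks under 1st post-therapy and tissue collection, and baseline is blank.

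**2. Does footnote 1 cover baseline?** It speaks of the research PET/CT and does not exclude baseline. If it includes baseline, the chart omits a review that its own footnote presupposes. Note 2 in section 2.2 uses a similar term for the 1st post-therapy scan alone. If footnote 1 is read that way, the baseline research scan has neither a mark nor an AE window. Either reading needs correction.

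**3. What is captured, by type of event?**

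| Event | Baseline research scan | 1st post-therapy scan |
|---|---|---|
| Serious, any cause, from consent to completion of biopsy | Reportable (7.2.1.1) | Reportable (7.2.1.1) |
| Serious and related to the procedure, any time | Reportable if it reaches the investigator | Reportable if it reaches the investigator |
| Non-serious, grade 3 or higher, during the session | No scheduled review | Reviewed |
| Non-serious, grade 3 or higher, scan-related, after the session | Outside the window | Outside the window |

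Consent precedes study procedures, so a baseline scan done for research always falls inside the window for serious events. The gaps are in the last two rows.

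**4. How many exposures lack a scheduled review?** Section 2.1 gives the maximum enrollment: "We anticipate enrolling up to 35 participants". Let *b* be the number of baselines done for research. If all 35 also have the 1st post-therapy scan, the share without a scheduled review is *b* / (*b* + 35).

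- All baselines research, *b* = 35: 35/70 = 50%.
- Assumed 80% research, *b* = 28: 28/63 = 44%.
- Usually taken as a bare majority, *b* = 18: 18/53 = 34%.

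The protocol does not give *b*, so the range is the honest answer. It moves little with dropout. If only the 30 evaluable patients reach the second scan and all 35 have a baseline scan, the ends become 18/48 = 38% and 35/65 = 54%. These shares count exposures without a mark on the chart. They do not count exposures without any safety reporting.

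**5. How long is the scan window?** Section 7.1.2.2 starts imaging about 60 minutes after injection, so the window is one visit. Bruising, dizziness and fainting can occur within it. Phlebitis and infection would mostly appear later.

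**The case against.** The strongest reply is that safety is not an objective or endpoint here. FDG is approved, is given by routine clinical procedure, and according to 4.1.1 has no reported AEs at this dose. Limited AE collection is therefore a defensible choice. Grade 3 as the protocol defines it overlaps heavily with its seriousness criteria, so many events that matter would be reportable as serious. All of this stands, and it is why the point is minor. It does not explain why one research scan is reviewed and the other is not.

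A reader might infer more than the documents support:

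- *That up to half of the research exposures have no safety assessment.* This does not follow. The serious-event window opens at consent and covers a baseline research scan. What is missing is scheduled review of non-serious events.
- *That the windows close before the named harms could appear.* Bruising, dizziness and fainting can occur during the session, and bleeding can occur during the biopsy. Only the delayed harms fall outside.
- *That biopsy harms are not captured.* The limit in footnote 1 applies to scan-related events only. AE review is marked at tissue collection, 7.2 applies standard AE reporting when a biopsy is taken, and related serious events are reportable at any time. At most, no end date is given.
- *That the missing end of the serious-event window for patients without a biopsy hides harms.* A window with no end collects too much, not too little. It is a drafting gap.
- *That a finding of no procedure-related AEs would be produced by the windows.* The plan proposes no such analysis, and serious events would still be reported.

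A patient who has the biopsy also gets an AE review after the 1st post-therapy scan, at tissue collection planned within 7 days. That helps, but as worded the time limit still excludes a delayed scan-related event found then, and not every patient has a biopsy.

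**Conclusion.** The point holds in a narrow form. Non-serious events of grade 3 or higher at a baseline research scan have no scheduled review, although the protocol treats that scan as a study exposure. This concerns roughly a third to a half of research FDG exposures (18/53 to 35/70), assuming that all 35 participants have both scans and that usually means at least 18 of 35 baselines. Separately, delayed non-serious scan-related events such as phlebitis or infection fall outside the window in footnote 1 and 7.1.2.1, and that window does not fit the broader definition and capture in 7.2.

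Severity is minor. The expected number of such events is small by the protocol's own account, serious events are covered, and the primary analysis, the sample size and all endpoints are untouched.

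**What to change.** - In 6.1, mark AE review under the baseline PET/CT when that scan is a research exam, and say in footnote 1 which scans it covers.
- Reconcile footnote 1 and 7.1.2.1 with 7.2 and 7.2.1.1, so that delayed procedure-related events at the recorded grades are captured for a stated period after each procedure. The sponsor should choose the length. Existing visits or the record review already planned in 7.1.4.2 can serve, so no new visit is needed.
- In 7.2.1.1, state when the window for serious events ends for patients who have no post-therapy biopsy.

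The cost is an amendment to wording, one more check at the baseline scan and at contacts that already take place, and a few more events to record.

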7.1.2.2 Tumor Imaging and Assessment of Disease

The following procedures will be done at each imaging session, as per routine clinical practice for FDG PET/CT imaging.

- Injection of FDG performed as per routine clinical procedure.

All women of child-bearing potential will be asked on the day of the PET/CT scan if they might be pregnant; this is a standard question for all patients who will be undergoing PET/CT scans due to the radiation exposure associated with the scan. If the patient is unsure about whether she might be pregnant then a urine pregnancy test will be performed prior to the injection of FDG.

The patient will be made comfortable in a preparatory room. Approximately 15 mCi of FDG will be administered according to the standard procedures used for clinical FDG PET/CT at the Hospital of the University of Pennsylvania. All patients will undergo a vertex of skull to toes PET/CT scan starting at approximately 60 minutes after FDG injection. A brief low-dose CT scan will be acquired according to standard PET/CT imaging procedures; this is used for attenuation correction and anatomical localization of findings in the PET scan. This can be performed either before or after the PET transmission scan. There are no separate diagnostic CT scans performed as part of this research.

A total of three FDG PET/CT exams will be performed as follows:

- Baseline: A restaging FDG PET/CT will be obtained no more than 4 weeks prior to initiation of pembrolizumab to assess baseline, pre-therapy tumor glycolytic activity. This exam will be obtained for study purposes, although in some cases it may be obtained as clinical standard of care for restaging of disease prior to initiation of a new line of therapy. If this exam is obtained as clinical standard of care, it may occur prior to consent and enrollment in this study.
- 1st Post-therapy: at approximately 3 weeks (\pm 3 weeks) following the start of pembrolizumab, a post-therapy FDG PET/CT will be obtained. This exam will be obtained for study purposes, to assess glycolytic activity at sites of metastatic disease at an early time-point.
- 2nd Post-therapy: When clinically indicated, as per the judgment of the patient's oncologist, a restaging FDG PET/CT will be obtained at $>$ 10 weeks following the start of pembrolizumab. This exam is clinical standard of care for restaging of disease after initiation of a new line of therapy, and would be performed even if the patient was not enrolled in the study. In some cases MRI or CT imaging may be performed as standard of care for restaging disease instead of FDG PET/CT.

